Diagnosis and Main Inclusion Criteria	Unresectable Stage III and Stage IV melanoma who are positive for NRAS mutation or who are BRAF/NRAS WT and failed or are ineligible for standard treatment options
Study Product, Dose, Route, Regimen	CDX-3379 – ERBB3 human monoclonal antibody: 15mg/kg IV every three weeks Trametinib (Mekinist®) – MEK inhibitor: 2 mg PO daily

CONFIDENTIAL

Duration of administration	CDX-3379 infusion every three weeks and trametinib orally daily until disease progression, intolerable side effects, patient choice, or study closure
Reference therapy	
Phase 2 results of response rates will be compared to results from the NEMO trial for NRAS mutant melanoma – single agent MEK inhibitor (binimetinib) compared to DTIC – and WT melanoma to results from a phase I trial of trametinib in WT melanoma.
 
For Phase 2 exploratory objectives, PFS can be compared where PFS was 2.8 months for trametinib compared to 1.5 months for DTIC in NRAS mutant melanoma and PFS was 2 months for trametinib in WT melanoma.

Statistical Methodology	
Phase 1b: Safety run in of the combination of CDX-3379 and trametinib and monitored for DLTs. If DLT occurs in 2 or more participants, then de-escalated cohorts will be evaluated. Six to 18 evaluable participants will be treated to identify the MTD/RP2D prior to advancing to phase 2.
 
Phase 2: There are two Arms of the study – Arm A: NRAS mutant melanoma patients, and Arm B: WT melanoma patients. This is the first part of a Simon Minimax design. Each Arm will initially enroll 19 patients. If, after the 19 patients in each cohort, there are two or fewer responses, the cohort will be stopped. Otherwise, the study will be amended to accrue a total of 36 to each arm (an additional 17 participants per arm). If a true response rate is 0.20, we will have a probability of 0.46 of stopping early and a probability of 0.90 of deciding that the treatment is useful.

CONFIDENTIAL

1 Introduction

This document is a protocol for a human research study. This study is to be conducted in accordance with US government research regulations, and applicable international standards of Good Clinical Practice, and institutional research policies and procedures.

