If two or more of the six subjects experience DLT, we will consider the initial dose cohort beyond the MTD and we will enroll six more patients in cohort 1A or 1B, based on the toxicity pattern observed that is felt to be attributed to a particular drug. Dose reduction to -1A or -2A is specifically for toxicity related to trametinib, LVEF reduction, RPED, pneumonitis and LFT abnormalities. -1A is the first reduction, followed by -2A as the second reduction. For all other observed toxicities the default dose-reduced cohort is -1B followed by -2B. In the new dose cohort, if none or one patient experiences a DLT, then the study will open to full enrollment on the Phase II portion of the trial. If two or more of these additional six patients experience DLT, we will then enroll six

CONFIDENTIAL

additional patients at additional dose de-escalation cohorts, to be determined by sponsor (NYULMC) and NYU DSMC), again based on toxicity pattern observed and drug attribution. If two or more patients experience DLT at this new dose cohort, then the trial will be terminated.

Phase 2: There are two Arms - Arm A (*NRAS* mutant melanoma patients) and Arm B (WT melanoma patients). This is the first part of a Simon Minimax design. Each arm will initially enroll 19 subjects. If there are three or fewer responses, then accrual to that cohort will be stopped. Otherwise, the study will be amended to enroll a total of 36 subjects to each approved arm/cohort.

Abbreviations: C = cycle; D = day; PD = progressive disease.

Figure 2: Phase II study design

Translational Research -

We will perform biopsies on all phase Ib patients (expected 6 patients, but could be up to 18) and five patients on each Arm of the study for Phase II. Biopsies will be obtained pre-treatment, on-treatment between day 14-16, and at the time of disease progression. Archival tissue will also be collected. We will investigate pathway inhibition of ERBB3 signaling and MAPK signaling pathways by analyzing components of the signaling pathways in addition to key components integral in these signaling pathways. We will also evaluate NRG1/HRG1 (neuregulin 1/heregulin 1, ERBB3 ligand) expression and correlate this with treatment response.

CONFIDENTIAL

This material is the property of the NYU School of Medicine and Langone Medical Center. Do not disclose or use except as authorized in writing by the study sponsor

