7.1 Sample Size Determination

For Phase 1b:

No data are available for the combination of CDX-3379 (ERBB3 antibody) and trametinib. Six subjects will be enrolled at an initial dose level – a safety run-in - and monitored for DLTs. In these six subjects, if none or one subject experiences a DLT, then dose cohort 1 will be considered the RP2D, and phase II of the clinical trial will proceed. If two or more of the six subjects experience DLT, we will consider the initial dose cohort beyond the MTD and we will enroll six more subjects on a de-escalated cohort, based on toxicity pattern observed attributed to a particular drug (Cohort -1A or -1B). In this new dose cohort, if none or one subject experiences a DLT, then the study will open to full enrollment on the Phase II portion of the trial. If two or more of these additional six subjects experience DLT, we will then enroll six additional subjects at an additional dose de-escalation cohort -2, to be determined by sponsor (NYUL Health) and DSMC), again based on toxicity pattern observed and drug attribution. If two or more subjects experience DLT at this new dose cohort, then the trial will be terminated.

For Phase 2: There are two Arms - Arm A (*NRAS* mutant melanoma participants) and Arm B (WT melanoma participants). This is the first part of a Simon Minimax design. Each Arm will initially enroll 19 patients. If there are two or fewer responses, the specific cohort will be stopped. Otherwise, the study will be amended to enroll a total of 36 patients to each approved Arm/cohort (an additional 17 patients per arm). If a true response rate is 0.20, we will have a probability of 0.46 of stopping early and a probability of 0.90 of deciding that the treatment is useful.

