7.2 Statistical Methods

Data collection will begin from time of enrollment and subjects will be followed until death (PFS and OS endpoints). If subjects are still alive, they will be censored at the time of evaluation. We will first investigate the association between biomarker expression and disease characteristics using t-test, ANOVA, or Chi-squared tests. We will then investigate the association between biomarker expression and PFS and OS using Kaplan-Meier approach and log rank test where biomarker expression is dichotomized. We may also use Cox proportional models to assess the association between biomarkers and outcome with adjustment for potential confounders such as disease characteristics. Biomarkers measured pre-, on-and post-treatment will be examined and are mainly exploratory at this time. Future tests will be derived from these results. For phase 2, the primary efficacy endpoint, response rate, will be compared with the historically reported response rate for the single agent trametinib in *NRAS* mutant and *BRAF/NRAS* WT melanoma. For secondary endpoints, we will estimate median PFS, OS and 95% CI using the Kaplan-Meier approach. In *NRAS* mutant melanoma patients treated with single agent MEK inhibitor, response rate was 15% and median PFS was 2.8 months¹⁵, and in *BRAF/NRAS* WT melanoma

CONFIDENTIAL

patients treated with single agent MEK inhibitor, response rate was 10% and median PFS was 2 months⁷

Assuming a true response rate of 0.20, Simon's two-stage Minimax design will test the null hypothesis that $RR \leq 0.20$; the sample size of 36 patients provides an alpha level of 0.10 and power of 0.80. Nineteen patients will be enrolled to the *NRAS* mutant arm of the study and 19 patients will be enrolled to the BRAF/*NRAS* WT arm of the study in the phase 2. If at least 3 patients respond (PR or better) out of 19 evaluable patients, then the study will be amended to enroll an additional 17 patients (for a total of 36 evaluable patients). If the Simon two-stage Minimax design is fully completed, a minimum of 10 patients must demonstrate a response (PR or better) to reject the null hypothesis.

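### At the null response rate of 0.20 the plan claims a 0.46 chance of stopping early and a 0.90 chance of success; the two cannot both hold, and the printed rules also miss the stated alpha

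*Combined protocol and SAP*

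**What the plan says.** The phase 2 design is described in four places.

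- **Study Summary (Statistical Methodology) and section 7.1.** Each arm enrols 19 patients. In the Summary's words, if "there are two or fewer responses, the cohort will be stopped"; section 7.1 has the same cut. Otherwise an amendment takes the arm to 36. Both places then give the operating characteristics: "If a true response rate is 0.20, we will have a probability of 0.46 of stopping early and a probability of 0.90 of deciding" in the treatment's favour.
- **Section 3.1.** Same sizes, different stage 1 cut: "If there are three or fewer responses, then accrual to that cohort will be stopped".
- **Section 7.2.** The null hypothesis is a response rate of at most 0.20. The sentence opens "Assuming a true response rate of 0.20" and goes on to say that "the sample size of 36 patients provides an alpha level of 0.10 and power of 0.80". The arm continues "If at least 3 patients respond (PR or better) out of 19 evaluable patients", and at the end "a minimum of 10 patients must demonstrate a response (PR or better) to reject the null hypothesis".

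No section gives an alternative response rate. The 15% and 10% in section 7.2 are historical single-agent rates, and both lie below the null.

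**The concern.** The Study Summary and section 7.1 attach two mutually exclusive outcomes to the same true rate, with probabilities that add to more than one. Because section 7.2 makes that rate the null, the chance of a positive verdict there should be near alpha, not 0.90. Power is given at two levels, and the only rate attached to either is the null itself.

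This matters in three ways.

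- A reader is told that an arm with a true 20% response rate will very probably be declared useful, when the printed rules do the opposite.
- The success rule does not hold the error rate the plan claims for it.
- The stage 1 cut differs between sections, so an arm with exactly 3 responses in 19 stops under section 3.1 and continues under the other three places. This version authorises only stage 1 (38 phase 2 patients), so that decision falls under the present text.

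**Working it through.** **Inputs.** Stage 1 size 19, total 36, so 17 in stage 2 (7.1). Stage 1 stops at r1 = 2 (Study Summary, 7.1, 7.2) or r1 = 3 (3.1). Success at s = 10 or more of 36 (7.2). Null rate 0.20 and alpha 0.10 (7.2).

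**Formulas.** X1 ~ Bin(19, p) and X2 ~ Bin(17, p), independent.

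- P(stop early) = P(X1 ≤ r1)
- P(useful) = sum over x > r1 of P(X1 = x) × P(X2 ≥ s − x)

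**1. The plan's 0.46.** At p = 0.20, P(X1 = 0, 1, 2, 3) = 0.0144, 0.0685, 0.1540, 0.2182.

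- r1 = 2: 0.0144 + 0.0685 + 0.1540 = 0.237
- r1 = 3: 0.237 + 0.218 = 0.455

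The 0.46 is reproduced only with section 3.1's cut.

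**2. The plan's 0.90.** The sum is 0.46 + 0.90 = 1.36, which is impossible for exclusive outcomes. Nor can any final cut rescue it, because P(useful) cannot exceed the chance of passing stage 1: 1 − 0.237 = 0.763, or 1 − 0.455 = 0.545.

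**3. Type I error at 10 of 36.** With p = 0.20 and r1 = 2:

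| Stage 1 responses x | P(X1 = x) | P(X2 ≥ 10 − x) | Product |
|---|---|---|---|
| 3 | 0.2182 | 0.0377 | 0.0082 |
| 4 | 0.2182 | 0.1057 | 0.0231 |
| 5 | 0.1636 | 0.2418 | 0.0396 |
| 6 | 0.0955 | 0.4511 | 0.0431 |
| 7 | 0.0443 | 0.6904 | 0.0306 |
| 8 | 0.0166 | 0.8818 | 0.0146 |
| 9 | 0.0051 | 0.9775 | 0.0050 |
| 10 or more | 0.0016 | 1 | 0.0016 |

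The total is 0.166. With r1 = 3 the first row drops out: 0.166 − 0.008 = 0.158. Both exceed 0.10.

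**4. All boundary pairs.** Success at 11 of 36 is printed nowhere, and the 0.40 column is an assumed rate.

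| Stop at / succeed at | Stop early, 0.20 | Useful, 0.20 | Useful, 0.30 | Useful, 0.40 |
|---|---|---|---|---|
| ≤2/19, ≥10/36 | 0.237 | 0.166 | 0.670 | 0.953 |
| ≤3/19, ≥10/36 | 0.455 | 0.158 | 0.651 | 0.944 |
| ≤2/19, ≥11/36 | 0.237 | 0.089 | 0.532 | 0.909 |
| ≤3/19, ≥11/36 | 0.455 | 0.086 | 0.523 | 0.902 |

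**5. Likely origin (inference only).** A Simon minimax search for 0.20 versus 0.40, alpha 0.10 and power 0.90 first succeeds at 36 patients: stop at ≤3/19, succeed at ≥11/36, type I error 0.086, power 0.902, early stopping 0.455. That reproduces 19, 36, 0.46 and 0.90. For power 0.80 against the same assumed 0.40, the search needs only 24 patients.

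**6. Decisions at stake.**

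- P(exactly 3 of 19) is 0.218 at 0.20 and 0.087 at 0.30.
- P(reaching stage 2 and ending at exactly 10 of 36) is 0.071 to 0.077 at 0.20 and 0.128 to 0.138 at 0.30, depending on the stage 1 cut.

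**The case against.** The 0.90 looks like a sentence that lost its alternative rate, the sample size is not shown to be wrong, and the phase 2 aim is worded as estimation. Three of the four places agree on the stage 1 cut, and no arm goes past 19 patients without an amendment that would itself be reviewed. Section 7.2 is the only place with a complete rule, and it gives 0.166; the 0.158 combines section 3.1's stage 1 cut with section 7.2's final cut. The 0.80 could also be correct power at some other unprinted rate: with success at 10 of 36 it is reached at a true rate of about 0.33 to 0.34.

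Much of this is fair, and it limits the practical harm. The 0.80 cannot be called wrong in itself; it simply has no rate attached. The amendment step means that the choice at 3 of 19 is between stopping and seeking 17 more patients, not automatic enrolment.

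None of it removes the error. Section 7.2 still sets a formal test with a null, an alpha and a rejection rule, and that rule misses its alpha under either stage 1 cut. Section 7.1's sentence is impossible on any reading: taking 0.20 as the alternative does not help, since P(useful) there is about 0.16. Section 7.2 leaves detail to a later SAP, but it also requires major changes to the primary analysis to appear in a protocol amendment.

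**Conclusion.** The concern holds, and the text must be corrected. At a true rate of 0.20 the plan states a 0.90 chance of a positive verdict; its printed rules give 0.158 to 0.166, so such an arm is declared not useful 83% to 84% of the time. The same figures are the type I error, against a stated 0.10. The 0.46 disagrees with the stage 1 cut printed beside it (0.237), and neither power figure has an alternative rate.

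These conclusions rest only on printed numbers and exact binomial arithmetic, with 19 and 36 evaluable patients per arm. The reconstruction with an alternative of 0.40 is an inference, and the verdict does not depend on it.

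**What to change.** In the Study Summary and section 7.1, remove 0.90 as a probability at 0.20. In section 7.2, remove 0.20 as the rate on which power is based, and replace 0.80 with the power at the stated alternative. Give the null as 0.20 and have the sponsor confirm the alternative; 0.40 is likely but undocumented. Then print one boundary pair in the Study Summary and sections 3.1, 7.1 and 7.2. Power below is at an assumed 0.40.

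| Option | Stop early, 0.20 | Type I error | Power | Edits to the boundaries |
|---|---|---|---|---|
| A: ≤3/19, ≥11/36 | 0.46 | 0.086 | 0.90 | Summary and 7.1 to three or fewer; 7.2 to at least 4 and a minimum of 11 |
| B: ≤2/19, ≥11/36 | 0.24 | 0.089 | 0.91 | 3.1 to two or fewer; 0.46 to 0.24; 7.2 to a minimum of 11 |
| C: ≤2/19, ≥10/36 | 0.24 | 0.166 | 0.95 | 3.1 to two or fewer; 0.46 to 0.24; alpha restated as 0.17 |

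A suitable sentence for the Study Summary and 7.1: *With a true response rate of 0.20, the arm stops early with probability [a] and is declared useful with probability [b]; with a true rate of [confirmed alternative], it is declared useful with probability [c].*

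**Cost.** Restating the figures is wording only, and the sizes stay at 19 and 36. Relative to ≤2/19 with ≥10/36, A gives up 0.953 − 0.902 = 0.051 of power at 0.40 and 0.670 − 0.523 = 0.147 at 0.30. B gives up 0.045 and 0.138. C gives up none but accepts a type I error of 0.166, so the description as an alpha-0.10 minimax design must go. B meets alpha 0.10 with a maximum of 36, but its expected size at 0.20 is 32.0 per arm against 28.3 for A. It is therefore not strictly the minimax design, and that label should be qualified if B is chosen. The stage 1 cut needs settling before either arm's first 19 patients are assessed; the final cut must be settled before stage 2 opens.

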7.2 Statistical Methods

Data collection will begin from time of enrollment and subjects will be followed until death (PFS and OS endpoints). If subjects are still alive, they will be censored at the time of evaluation. We will first investigate the association between biomarker expression and disease characteristics using t-test, ANOVA, or Chi-squared tests. We will then investigate the association between biomarker expression and PFS and OS using Kaplan-Meier approach and log rank test where biomarker expression is dichotomized. We may also use Cox proportional models to assess the association between biomarkers and outcome with adjustment for potential confounders such as disease characteristics. Biomarkers measured pre-, on-and post-treatment will be examined and are mainly exploratory at this time. Future tests will be derived from these results. For phase 2, the primary efficacy endpoint, response rate, will be compared with the historically reported response rate for the single agent trametinib in *NRAS* mutant and *BRAF/NRAS* WT melanoma. For secondary endpoints, we will estimate median PFS, OS and 95% CI using the Kaplan-Meier approach. In *NRAS* mutant melanoma patients treated with single agent MEK inhibitor, response rate was 15% and median PFS was 2.8 months¹⁵, and in *BRAF/NRAS* WT melanoma

CONFIDENTIAL

patients treated with single agent MEK inhibitor, response rate was 10% and median PFS was 2 months⁷

Assuming a true response rate of 0.20, Simon's two-stage Minimax design will test the null hypothesis that $RR \leq 0.20$; the sample size of 36 patients provides an alpha level of 0.10 and power of 0.80. Nineteen patients will be enrolled to the *NRAS* mutant arm of the study and 19 patients will be enrolled to the BRAF/*NRAS* WT arm of the study in the phase 2. If at least 3 patients respond (PR or better) out of 19 evaluable patients, then the study will be amended to enroll an additional 17 patients (for a total of 36 evaluable patients). If the Simon two-stage Minimax design is fully completed, a minimum of 10 patients must demonstrate a response (PR or better) to reject the null hypothesis.

Detailed methodology for summary and statistical analyses of the data collected in this study will be documented in a Statistical Analysis Plan (SAP), which will be dated and completed prior to database lock. The SAP may modify the plans outlined in the protocol; however, any major modifications of the primary endpoint and/or its analysis will also be reflected in a protocol amendment.

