3.1 General Design

This study is an open-label, non-randomized phase Ib/II study in patients with unresectable stage III or stage IV *NRAS* mutant or *BRAF/NRAS* WT melanoma.

Following signing informed consent and evaluation of initial eligibility criteria, all participants will provide an archived tissue sample (which meets the requirements for collection and processing as outlined in the study lab manual). In addition, all patients enrolled on Phase Ib and the first five *NRAS* mutant melanoma participants and first five WT melanoma participants on Phase II will undergo a mandatory core biopsy for pretreatment tumor tissue. For these procedures, investigators are asked to choose an easily accessible tumor lesion to minimize any possible risk associated with the collection of the tissue. As a general guideline, if the selected procedural location of the core needle biopsy or FNA has an established serious complication rate of >2% at the institution completing the procedure, this is considered a high risk procedure and should be avoided.

The purpose of this phase Ib study is to determine the MTD/RP2D and assess the toxicity and tolerability of combination of CDX-3379 (ERBB3 inhibitor) and trametinib (MEK inhibitor) in *NRAS* mutant and WT advanced stage melanoma. The purpose of phase II study is to estimate the response rate and duration of response of the combination in each cohort of participants that are *NRAS* mutant and WT advanced stage melanoma

Abbreviations: C = cycle; D = day; PD = progressive disease.

Figure 1: Phase Ib study design

Phase 1b: 6-18 evaluable subjects will be treated to identify the MTD/RP2D prior to advancing to phase II.

CONFIDENTIAL

This material is the property of the NYU School of Medicine and Langone Medical Center. Do not disclose or use except as authorized in writing by the study sponsor

Definition of MTD/RP2D -

Once the subject has completed the screening procedures and is deemed eligible for the study, the subjects will be assigned to the following therapy:

Trametinib: 2 mg PO daily
ERBB3 antibody (CDX-3379) 15mg/kg IV on day 1 of each 21-day cycle

MTD/RPRD will be determined by combining ERBB3 antibody (CDX-3379) 15mg/kg IV Q3W with 2mg trametinib. Dose de-escalation of ERBB3 antibody (CDX-3379) and/or trametinib, if needed, will be allowed if significant toxicity is experienced with the two drugs at their recommended doses (which were previously determined).

Cohort levels for MTD/RP2D:

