4.1 Inclusion Criteria

1. Read, understood, and provided written informed consent and, if applicable, Health Insurance Portability and Accountability Act (HIPAA) authorization after the nature of the study has been fully explained and must be willing to comply with all study requirements and procedures.
2. Male or female patients who are 18 years of age or older.
3. Patients with a diagnosis of histologically confirmed advanced (defined as unresectable stage III or IV) melanoma with the *NRAS* Q61 mutation or *BRAF/NRAS* WT who are refractory to or intolerant of existing therap(ies) known to provide clinical benefit for their condition, including anti PD-1 and/or CTLA-4 agent.
 - Any CLIA certified mutation testing is acceptable to document mutation status.
4. Patients must have adequate cardiac function as demonstrated by a left ventricular ejection fraction (LVEF) $\geq 50\%$ as determined by a multigated acquisition (MUGA) scan or echocardiogram.
5. Patients must have archival tissue and at least one disease site amenable to biopsy:
 - For phase Ib, all patients will undergo fresh tumor biopsy
 - For phase II, five patients with *NRAS* mutation and five patients with *BRAF/NRAS* WT melanoma will undergo fresh tumor biopsy
6. Measurable (target) disease by Response Evaluation Criteria In Solid Tumors (RECIST 1.1) criteria. Target lesions selected for tumor measurements should be those where additional (eg palliative) treatments are not indicated or anticipated.
 - Measurable disease per RECIST 1.1 requirements: defined as longest diameter to be recorded for non-nodal lesions $> 10\text{mm}$ and short axis for nodal lesions $> 15\text{ mm}$ using conventional techniques
7. All residual toxicity related to prior radiotherapy or anticancer therapies (excluding alopecia, grade 2 fatigue, vitiligo or endocrinopathies on stable replacement therapy) must resolve to grade 1 severity or less (or returned to baseline) prior to receipt of study treatment.
8. Adequate electrolytes, liver, renal, and hematology function as defined below:
 - a. Hemoglobin $\geq 9\text{ g/dL}$
 - b. Absolute neutrophil count $\geq 1500/\text{mm}^3$
 - c. Platelet count $\geq 100,000/\text{mm}^3$
 - d. Aspartate aminotransferase (AST) and alanine aminotransferase (ALT) $\leq 2.5 \times$ upper limit of normal (ULN) ($\leq 5 \times$ ULN for cases involving liver metastasis)
 - e. Bilirubin $\leq 1.5 \times$ ULN ($\leq 5 \times$ ULN for cases of documented or suspected Gilbert's disease)

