5.10 Biomarker Samples

Biomarker data will be explored from archived tissue and pre-treatment, on-treatment, and disease progression tumor biopsy samples during Phase Ib and from ten subjects during the Phase II portion of the study (five subjects with *NRAS* mutation and five subjects with BRAF/*NRAS* WT melanoma), to assess potential associations with tumor response. These samples will be collected prior to treatment on cycle 1 day 1, on day 14-16 after initial treatment, and at the time of disease progression. These samples will be used to assess additional clinically relevant biomarkers, including but not limited to expression levels of ERBB3, cMET, ERBB2, and EGFR and will include assessment of respective receptor ligands. Efficacy outcomes considered for pre-specified mechanistic biomarker analysis will include PFS, objective response rate, and OS based on investigator assessments.

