5.10.1 Archived Tumor Samples

If available, formalin-fixed paraffin embedded tumor samples (either a tumor block or freshly cut slides) from the patient's most recent tumor sampling will be collected for biomarker analysis. Tumor samples obtained at the time of metastasis are preferred over tumor samples obtained at the time of primary diagnosis; however, in the event that both are available for analysis, we ask that samples from both time points should be submitted. Directions and requirements for processing and shipping the archived tumor samples can be found in the laboratory manual.

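### The planned PFS and OS biomarker test splits expression at an unstated cut; a continuous or ordered Cox model, with any cut fixed in advance, would be a cheap improvement

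*Combined protocol and SAP*

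**What the plan says.** Section 7.2 (Statistical Methods) first relates biomarker expression to disease characteristics. It then relates expression to PFS and OS by Kaplan-Meier and a "log rank test where biomarker expression is dichotomized". No cut point, rule for choosing one, or reason for splitting is given. The section adds: "We may also use Cox proportional models to assess the association between biomarkers and outcome", in the context of adjusting for confounders, without saying whether the marker would be continuous or two-level. The biomarker measurements "are mainly exploratory at this time", and later tests are to be built on what is found. Further detail is left to a separate SAP, to be completed before database lock.

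On who has biomarker data, section 3.1 says: "We will perform biopsies on all phase Ib patients (expected 6 patients, but could be up to 18) and five patients on each Arm". Section 5.10 agrees for phase II: "from ten subjects during the Phase II portion of the study". For archival tissue, section 3.1 says "all participants will provide an archived tissue sample", and section 4.1 makes it an entry criterion: "Patients must have archival tissue and at least one disease site amenable to biopsy". Section 5.10.1, however, begins "If available, formalin-fixed paraffin embedded tumor samples". Sections 2 and 5.10 can also be read as limiting archival collection to the biopsied subset.

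**The concern.** Splitting a measured marker into high and low treats every patient on one side of the cut as equal. When the marker's effect is graded, this loses power, and the fresh-biopsy set has few patients to spare.

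The unstated cut is the second problem. In an open-label study, a cut chosen after outcomes are known can be chosen because it gives a small p-value. Section 3.4 names 15 candidate markers and leaves the list open, and samples are taken before treatment, on treatment and at progression, so the opportunity recurs often. Section 5.10 describes the efficacy outcomes as feeding a pre-specified biomarker analysis; a test without a stated cut is not fully pre-specified.

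What is at stake is which markers are carried forward.

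**Working it through.** The documents give no sample size, alpha, effect size or cut for this analysis, so there is no planned figure to reproduce. Alpha (two-sided 0.05), the effect sizes and an event in every patient are assumptions.

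**Patients.** Fresh biopsies: 6 + 10 = 16, up to 18 + 10 = 28. Archival tissue, if everyone supplies it: 6 + 38 = 44, up to 18 + 38 = 56.

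**Information kept by a split.** For a normal marker with a log-linear effect, cut at quantile q, relative efficiency is φ(z_q)² / [q(1 − q)]. At the median this is 2/π = 0.637, a loss of 36%. Other cuts lose 38% (40/60), 42% (30/70), 46% (25/75), 51% (20/80) and 66% (10/90). At the median, 16 to 28 patients carry the information of 16 × 0.637 ≈ 10 to 28 × 0.637 ≈ 18.

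**Power by formula.** Power = Φ(β√(events × efficiency) − 1.96), with β = 0.7 per SD:
- 16 events: continuous Φ(2.80 − 1.96) = 0.80; split Φ(2.23 − 1.96) = 0.61.
- 28 events: continuous Φ(3.70 − 1.96) = 0.96; split Φ(2.96 − 1.96) = 0.84.

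**Power by simulation.** The formula is a large-sample one, so it was checked with a Cox score test on the continuous marker against a log-rank test split at the sample median (normal marker, exponential times, no censoring, 40,000 runs):

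| Effect per SD | n | Continuous | Median split |
|---|---|---|---|
| log HR 0.7 | 16 | 0.61 | 0.42 |
| log HR 0.7 | 28 | 0.87 | 0.68 |
| HR 1.5 | 16 | 0.29 | 0.21 |
| HR 1.5 | 28 | 0.48 | 0.34 |
| HR 1.5 | 44 | 0.69 | 0.49 |
| HR 1.5 | 56 | 0.79 | 0.60 |

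Smaller independent runs agree to within about 0.02. The formula is too optimistic at these sizes, so the simulated figures should be used. The gain from keeping the marker continuous is about 8 to 20 percentage points.

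**Smallest effect the split can find.** With 80% power and equal groups, HR = exp[(1.96 + 0.842)/√(events/4)]: 4.1 at 16 events, 2.9 at 28, 2.3 at 44 and 2.1 at 56.

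**Searching for the cut.** With no marker effect, taking the best log-rank result over cuts from roughly the 20th to the 80th percentile gave nominal 5% significance in about 27 to 28% of runs at n = 16, 30 to 31% at n = 28 and 32% at n = 44. A median cut fixed in advance gave about 6 to 7%.

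**If the effect is a threshold.** The true threshold was placed at the population median, with log HR 1.4 between the groups:
- Split at the sample median: about 0.47 against 0.42 continuous at n = 16, and 0.75 against 0.69 at n = 28. Across runs, the split gains about 4 to 7 points.
- Split exactly at the true threshold: about 0.67 against 0.42 at n = 16, and 0.91 against 0.69 at n = 28, a gain of 22 to 25 points.

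**The case against.** The analysis is labelled exploratory, detail is deferred to an SAP that may modify the protocol's plans, and section 7.2 already permits Cox models in which the marker could be continuous. The dichotomization wording can even be read as conditional, with log-rank used only where a marker happens to be split. All of this limits the weight of the point. It does not settle it: log-rank on a split marker is the only PFS/OS test the section commits to, Cox is optional, and neither the coding nor the cut is given.

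The assays in section 3.1 (immunohistochemistry, Western blot, in situ hybridization) come without a scoring scale. If scores are ordinal or positive/negative, the 36% figure does not apply. That is a fair limit, though an ordered score can still enter a Cox model as a trend.

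The strongest objection is biological. Section 1.3.1 reports that adding CDX-3379 enhanced activity in BRAF-mutated models that express NRG but not in those that lack it, and section 1.1.3 contrasts cell lines with and without NRG1. If the effect is present/absent, a split is the better test, by a wide margin when the cut falls exactly on the threshold. This stands as a real cost. But that advantage needs the right cut named in advance, which the plan does not do.

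**Conclusion.** The point holds as a cheap improvement of low severity. Section 7.2 commits to a split marker at an unstated cut where a continuous or ordered analysis would usually be more informative. For a roughly normal marker with a graded effect and a median cut, the loss is about 36% of the information, or about 8 to 20 points of power over the effects and sample sizes examined. These figures assume an event in every patient. Fewer events, as is likely for OS, would lower power for both methods.

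Three stronger readings are not supported:
- A reader might infer that only 16 to 28 patients can enter these tests. That range counts fresh biopsies. It binds on-treatment and progression markers, but the archival provisions could give baseline expression in about 44 to 56. The wording on archival tissue must be reconciled before the denominator is known.
- A reader might take a loss of about a third as a fixed property of the plan. It depends on the marker's distribution, the form of the effect and the cut, none of which the documents state.
- A reader might think the change costs nothing. Under a threshold effect, the continuous model loses about 4 to 7 points against a sample-median split, and over 20 against a cut placed exactly on the threshold.

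No primary or secondary conclusion or stopping rule depends on this analysis.

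**What to change.** In the SAP:
- Make a Cox model with expression as a continuous covariate (log-transformed or standardised), or as an ordered score if the assay is ordinal, the main exploratory analysis of PFS and OS.
- Fix one cut per marker before outcomes are examined, for example the median, or present/absent for NRG1 where the rationale points that way. Use it for Kaplan-Meier display and a supportive log-rank test. Keeping that test protects against the threshold case.
- State each assay's scoring scale, and whether archival or fresh tissue supplies baseline expression. Reconcile sections 2, 3.1, 4.1, 5.10 and 5.10.1 on who provides archival tissue.

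The analysis change is SAP wording and needs no extra patients, samples or visits. Section 7.2 reserves protocol amendment for major changes to the primary endpoint or its analysis, which this is not; reconciling the archival text would be a minor protocol clarification. The statistical cost is the power loss under a threshold effect described above.
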